#### **Amendment History:**

Date	Amendment Number	Amendment Type	Region
19 September 2024	Amendment 2 US v1	Substantial; Regional	United States
03 April 2024	Amendment 1 v2	Substantial	Global
28 February 2024	Amendment 1 v1 (not implemented)	Substantial	Global
15 September 2023	Initial Protocol US v1	Nonsubstantial; Regional	United States
23 June 2023	Initial Protocol GB v1	Nonsubstantial; Regional	United Kingdom
05 April 2023	Initial Protocol DE v2	Nonsubstantial; Regional	Germany
05 April 2023	Initial Protocol DE v1	Nonsubstantial; Regional	Germany
27 January 2023	Initial Protocol CZ v1	Nonsubstantial; Regional	Czech Republic
14 December 2022	Initial Protocol FR v1	Nonsubstantial; Regional	France
16 August 2022	Initial protocol	Not applicable	Global

### 1.3 Protocol Amendment 2 US v1 Summary of Changes

#### Protocol Amendment 2 US v1 Summary and Rationale

This section describes the changes in reference to the protocol incorporating Amendment 2 US v1. The primary reason for this amendment was to include the United States Food and Drug Administration (FDA) recommendation of excluding patients with a high risk of bleeding events, including those on anticoagulation [REDACTED]  
[REDACTED]

In this amendment, minor grammatical, editorial, formatting, and administrative changes not affecting the conduct of the study are included for clarification and administrative purposes only.

A summary of changes for all prior protocol amendments is found in [Appendix G](#).

Protocol Amendment 2 US v1			
Summary of Changes Since the Last Implemented Version of the Approved Protocol			
Change Number	Section(s) Affected by Change	Description of Each Change and Rationale	
	Location	Description	Rationale
1.	7.2 Exclusion Criteria	Added exclusion criterion #11: "Patient has a high risk of hemorrhage such as uncontrolled chronic bleeding disorder or is currently being treated with therapeutic anticoagulation."	Revised per FDA recommendation
2.	[REDACTED] [REDACTED]	[REDACTED] [REDACTED] [REDACTED] [REDACTED] [REDACTED] [REDACTED] [REDACTED] [REDACTED] [REDACTED] [REDACTED] [REDACTED]	Revised per FDA recommendation

FDA: Food and Drug Administration; TEAE: treatment-emergent adverse event.

## **2.0 STUDY SUMMARY**

Name of Sponsor(s): Takeda Development Center Americas, Inc	Compound: Modakafusp alfa (TAK-573)
Title of Protocol: A Phase 1/2a Open-label Study to Evaluate the Safety, Tolerability, Pharmacokinetics, Pharmacodynamics, and Efficacy of Modakafusp Alfa in Combination With Daratumumab Subcutaneous in Patients With Relapsed or Refractory Multiple Myeloma	EudraCT No.: 2022-002169-14
Study Number: TAK-573-2001	Phase: 1/2a
Study Design:  This is a global multicenter, open-label, phase 1/2a study designed to evaluate the safety, tolerability, pharmacokinetics (PK), pharmacodynamics (PD), and preliminary efficacy of modakafusp alfa in combination with daratumumab subcutaneous (SC) in patients with relapsed or refractory multiple myeloma (RRMM). The study will begin with a phase 1 dose escalation to evaluate the safety and tolerability of modakafusp alfa in combination with daratumumab SC. Two dose levels of modakafusp alfa in combination with daratumumab SC will be selected to be further explored in the randomized phase 2a dose finding part of the study. Patients will be randomized in a 1:1 ratio across 2 dose levels (DL1 or DL2) of modakafusp alfa in combination with daratumumab SC. The confirmed overall response rate (ORR) assessed by the investigator per International Myeloma Working Group (IMWG) criteria will be determined as the primary efficacy endpoint of the phase 2a dose finding. The optimized recommended phase 2 dose (RP2D) of modakafusp in combination with daratumumab SC will be selected on the basis of integrated safety, efficacy, PK, and PD data from the current study and other relevant stud(ies). A schematic of the study design is shown below.	

DL1: Dose Level 1; DL2: Dose Level 2; Q4W: every 4 weeks; R: randomization; SC: subcutaneous.

#### Phase 1 Dose Escalation

The study will begin with a phase 1 dose escalation to evaluate the safety and tolerability of modakafusp alfa in combination with daratumumab SC during the Cycle 1 (28 days per cycle) dose-limiting toxicity (DLT) evaluation period and beyond. The proposed population in the phase 1 dose escalation will be patients with RRMM with at least 3 prior lines of therapy, including at least 1 proteasome inhibitor (PI), 1 immunomodulatory imide drug (IMiD), and 1 anti-CD38 monoclonal antibody (mAb) drug; or who are triple refractory to a PI, an IMiD, and an anti-CD38 mAb drug, regardless of the number of prior line(s) or therapy.

The dose escalation will follow the rolling six design with data collected in the dose escalation/de-escalation phase. Safety will be evaluated by the frequency of adverse events (AEs), severity, types of AEs, and by changes from baseline in patients' vital signs, weights, and clinical laboratory results.

The starting dose to be evaluated for modakafusp alfa will be 80 mg every 4 weeks (Q4W). Modakafusp alfa doses of 60, 120, or 240 mg Q4W could be evaluated depending on dose escalation/de-escalation rules specified by the rolling six design. Decision on dose escalation and de-escalation in phase 1 will be made on the basis of the number of patients in the current dose level, the number of patients experiencing DLTs, and the number of patients still at risk of developing a DLT at the time of a new patient entry. Three to 6 patients may concurrently be enrolled at a dose level in the study. The enrollment of the first 3 patients at the starting dose of 80 mg Q4W will be staggered by 24 hours each. The remaining patients can be dosed concurrently if there are no unexpected and significant acute toxicities. Accrual to the study may be paused while waiting for data from these 6 patients. Decisions as to whether to resume enrolling on the next dose level will be made using data available at the time of new patient enrollment. De-escalation will occur when 2 or more DLTs are observed at the current dose level,

whereas escalation will occur when 3 of 3, 4 of 4, 5 of 5, 5 of 6, or 6 of 6 patients are enrolled at the current dose level with no DLT observed and the next higher dose level has no more than 1 DLT observed. It is estimated that approximately 18 DLT-evaluable patients will be enrolled.

The daratumumab SC dose of 1800 mg (every week [QW] in Cycles 1 and 2, once every 2 weeks [Q2W] in Cycles 3 to 6, and Q4W thereafter) will be used in combination with modakafusp alfa throughout the study.

#### Phase 2a Dose Finding

Two dose levels of modakafusp alfa in combination with daratumumab SC doses will be selected from phase 1 dose escalation to be explored further in phase 2a open-label dose finding. Approximately 40 patients will be randomized 1:1 across 2 different dose levels (DL1 or DL2; N = 20 at each dose level) of modakafusp alfa in combination with daratumumab SC. Eligible patients will include patients with RRMM who have received 1 to 3 prior lines of therapy, refractory to lenalidomide, and sensitive (nonrefractory) or naive to anti-CD38 mAb. The randomization will be stratified by the number of prior lines of therapy (1 vs 2 or 3). The primary endpoint is the confirmed ORR assessed by the investigator per IMWG criteria.

#### **Primary Objectives:**

##### Phase 1 Dose Escalation

- To determine the safety and tolerability of modakafusp alfa in combination with daratumumab SC.

##### Phase 2a Dose Finding

- To inform the RP2D of modakafusp alfa in combination with daratumumab SC.
- To provide a preliminary evaluation of the clinical efficacy of modakafusp alfa in combination with daratumumab SC as measured by ORR.

#### **Secondary Objectives:**

##### Phase 1 Dose Escalation

- To characterize the PK profile of modakafusp alfa and daratumumab in the combination setting.
- To characterize antimyeloma activity as measured by ORR, duration of response (DOR), progression-free survival (PFS), and overall survival (OS).
- To characterize the immunogenicity of modakafusp alfa in combination with daratumumab SC.
- To characterize measurable (minimal) residual disease (MRD) negativity and duration of MRD negativity.

##### Phase 2a Dose Finding

- To determine DOR, clinical benefit rate (CBR), duration of clinical benefit (DCB), disease control rate (DCR), duration of disease control, time to progression (TTP), time to response (TTR), time to next treatment (TTNT), PFS, and OS.
- To further characterize safety and tolerability of modakafusp alfa in combination with daratumumab SC.
- To collect PK data for modakafusp alfa to support population PK and exposure-response analysis.
- To collect PK data for daratumumab SC to assess any potential impact of immunogenicity on daratumumab PK.
- To further characterize the immunogenicity of modakafusp alfa in combination with daratumumab SC.
- To characterize MRD negativity and duration of MRD negativity.

#### **Patient Population:** Patients aged 18 years or older with RRMM.

##### **Number of Patients:**

Phase 1 dose escalation: approximately 18 patients.

Phase 2a dose finding: approximately 40 patients.

A total of approximately 58 patients will be enrolled in this study.

##### **Number of Sites:**

Approximately 30 investigational centers globally.

Dose Level(s): Modakafusp alfa: Phase 1 dose escalation: 60, 80 (starting dose), 120, or 240 mg Q4W in 28-day cycles. Phase 2a dose finding: 2 dose levels (DL1 and DL2) selected after the phase 1 dose escalation. Daratumumab SC: 1800 mg QW for Cycles 1 and 2, Q2W for Cycles 3 to 6, and Q4W thereafter in 28-day cycles.	Route of Administration: Modakafusp alfa: Intravenous Daratumumab: SC
Duration of Treatment: Patients may receive study drug treatment until they experience progressive disease, unacceptable toxicity, or other discontinuation criteria are met.	Period of Evaluation: The study is expected to enroll patients for approximately 12 to 18 months (phase 1 and phase 2a) and continue follow-up for a total study duration of approximately 60 months.

Main Criteria for Inclusion: Each patient must meet all the following inclusion criteria to be enrolled in the study:
 

1. Patients aged 18 years or older.

2. Documented MM diagnosis per IMWG criteria.

3. Measurable disease, defined as at least 1 of the following:

a. Serum M protein <math>\geq 0.5</math> g/dL (<math>\geq 5</math> g/L) on serum protein electrophoresis.

b. Urine M protein <math>\geq 200</math> mg/24 hours on urine protein electrophoresis (UPEP).

c. Serum free light chain (FLC) assay with involved FLC level <math>\geq 10</math> mg/dL (<math>\geq 100</math> mg/L) provided serum FLC ratio is abnormal.

4. For patients in the phase 1 dose escalation only: Must have received at least 3 prior lines of therapy, including at least 1 PI, 1 IMiD, and 1 anti-CD38 mAb drug; or who are triple refractory to a PI, an IMiD, and an anti-CD38 mAb drug, regardless of the number of prior line(s) or therapy.

5. For patients in phase 2a dose finding only:

a. Received 1 to 3 prior line(s) of antimyeloma therapy.

b. Must be refractory to prior lenalidomide treatment.

c. Patients must be sensitive (nonrefractory) or naïve to prior anti-CD38 mAb treatment.

d. Documented progressive disease on or after the last regimen.

e. Patients must have partial response (PR) or better to at least 1 line of prior therapy.

 
Note: A line of therapy consists of <math>\geq 1</math> complete cycle of a single agent, a regimen consisting of a combination of several drugs, or a planned sequential therapy of various regimens (eg, 3 to 6 cycles of initial therapy with bortezomib-dexamethasone followed by a stem cell transplantation, consolidation, and maintenance is considered 1 line). Refractory myeloma is defined as disease that is nonresponsive while on therapy or progresses within 60 days of last therapy. Nonresponsive disease is defined as either failure to achieve at least minimal response or development of progressive disease while on therapy.
	

**Main Criteria for Exclusion:**

1. Prior exposure to modakafusp alfa.
2. Patient has POEMS (polyneuropathy, organomegaly, endocrinopathy, monoclonal gammopathy, and skin changes) syndrome, solitary plasmacytoma, amyloidosis, Waldenström macroglobulinemia, plasma cell leukemia, or lymphoplasmacytic lymphoma.
3. Patient has not recovered from adverse reactions to prior myeloma treatment or procedures (chemotherapy, immunotherapy, radiation therapy) to National Cancer Institute Common Terminology Criteria for Adverse Events (NCI CTCAE), Version 5 Grade  $\leq 1$  or baseline, except for alopecia.
4. Previous allogeneic stem cell transplant at any time or autologous stem cell transplant within 12 weeks of planned start of dosing.
5. Another malignancy within the previous 3 years, except treated basal cell or localized squamous skin carcinomas, localized prostate cancer, cervical carcinoma in situ, resected colorectal adenomatous polyps, breast cancer in situ, or other malignancy for which the patient is not on active anticancer therapy and that in the opinion of the local investigator, with concurrence with the sponsor, is considered to have minimal risk of recurrence within 3 years.

**Endpoints:****Primary Endpoints:****Phase 1 Dose Escalation:**

- DLT incidences.
- Frequency and severity of treatment-emergent adverse events (TEAEs) according to the NCI CTCAE, Version 5.0.

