#### **4.4 Modakafusp Alfa Dose Selection for Phase 2a Dose Finding in Combination With Daratumumab SC**

After the phase 1 dose escalation of modakafusp alfa in combination with daratumumab SC is completed, 2 modakafusp alfa dose levels will be selected for the 1:1 randomized phase 2a dose finding in combination with daratumumab SC.

The selection of 2 dose levels of modakafusp alfa in combination with daratumumab SC for the phase 2a dose finding will be made on the basis of the overall assessment of the results from the following:

1. The rolling six recommended tolerable doses in the phase 1 dose escalation based on DLT data in Cycle 1.
2. Additional safety, tolerability, PK, and PD data as available from Cycle 1 and beyond in the phase 1 dose escalation.

3. The benefit-risk assessment for 120 mg Q4W and 240 mg Q4W based on emerging efficacy and safety data from the phase 2, Part 3 extension of the separate ongoing modakafusp alfa monotherapy study (Study TAK-573-1501).

Therefore, integrated PK, PD, efficacy, and safety data analyses will be conducted using the phase 1 dose escalation data in combination with daratumumab SC and single-agent data from Study TAK-573-1501, Part 3 extension to select the 2 dose levels of modakafusp alfa in combination with daratumumab SC in the phase 2 dose finding.

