**Table 6.a Primary and Secondary Endpoints for Disclosures**

Endpoint	Definition	Maximum Time Frame
Phase 1 Dose Escalation		
Primary: DLT incidences	Section 8.3.1	Up to 60 months
Primary: Frequency and severity of TEAEs	Section 13.1.8	Up to 60 months
Secondary: Summary PK statistics for modakafusp alfa in Cycles 1 and 2	Sections 5.2.2 and 13.1.4	Up to 60 months
Secondary: Summary PK statistics for daratumumab in Cycles 1 and 2	Sections 5.2.2 and 13.1.4	Up to 60 months
Secondary: ORR by investigator	Section 13.1.3.1	Up to 60 months
Secondary: DOR by investigator	Section 13.1.3.2.1	Up to 60 months
Secondary: PFS by investigator	Section 13.1.3.2.1	Up to 60 months
Secondary: OS	Section 13.1.3.2.1	Up to 60 months
Secondary: ADA incidence and characteristics and NAb	Section 13.1.7	Up to 60 months
Secondary: Rate of MRD[-] CR by investigator	Section 13.1.3.2.1	Up to 60 months
Secondary: Rate of MRD[-]	Section 13.1.3.2.1	Up to 60 months
Secondary: Duration of MRD negativity	Section 13.1.3.2.1	Up to 60 months
Phase 2a Dose Finding		
Primary: ORR	Section 13.1.3.1	Up to 60 months
Secondary: DOR by investigator	Section 13.1.3.2.2	Up to 60 months
Secondary: CBR by investigator	Section 13.1.3.2.2	Up to 60 months
Secondary: DCB by investigator	Section 13.1.3.2.2	Up to 60 months
Secondary: DCR (CBR + SD) by investigator	Section 13.1.3.2.2	Up to 60 months
Secondary: Duration of disease control by investigator	Section 13.1.3.2.2	Up to 60 months
Secondary: TTP by investigator	Section 13.1.3.2.2	Up to 60 months
Secondary: TTR by investigator	Section 13.1.3.2.2	Up to 60 months
Secondary: TTNT	Section 13.1.3.2.2	Up to 60 months
Secondary: PFS by investigator	Section 13.1.3.2.2	Up to 60 months
Secondary: OS	Section 13.1.3.2.2	Up to 60 months
Secondary: Frequency and severity of TEAEs	Section 13.1.8	Up to 60 months
Secondary: ADA incidence and characteristics and NAb	Section 13.1.7	Up to 60 months
Secondary: Rate of MRD[-] CR by investigator	Section 13.1.3.2.2	Up to 60 months
Secondary: Rate of MRD[-]	Section 13.1.3.2.2	Up to 60 months
Secondary: Duration of MRD negativity	Section 13.1.3.2.2	Up to 60 months

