### **13.1.8 Safety Analysis**

AEs will be summarized using the safety population.

Safety will be evaluated by the frequency of AEs, severity, and types of AEs, and by changes from baseline in patients' vital signs, weights, ECOG performance status, ECG results, and clinical laboratory results using the safety analysis set.

Exposure to study drug over time will be summarized with time on treatment, total amount of administered treatment, dose intensity, and relative dose intensity. Reasons for treatment discontinuation and modification will be tabulated.

TEAEs that occur after administration of the first dose of study drug and through 30 days after the last dose of study drug or start of subsequent anticancer therapy, whichever occurs first will be tabulated. All AEs will be coded using the Medical Dictionary for Regulatory Activities. Data will be summarized using Preferred Term and/or primary System Organ Class and will include the following categories:

- TEAEs.
- Drug-related TEAEs.
- Grade 3 or higher TEAEs.
- Grade 3 or higher drug-related TEAEs.
- Grade 5 TEAEs.
- Grade 5 drug-related TEAEs.
- The most commonly reported TEAEs (ie, those reported by  $\geq 10\%$  of all patients).
- SAEs (related and regardless of relationship).
- SAEs Grade 3 or higher.
- Drug-related SAEs Grade 3 or higher.
- AESIs Grade 3 or higher.
- TEAE leading to study drug modification and discontinuation.

The incidence of DLTs will be tabulated using the DLT-evaluable population.

Descriptive statistics for the actual values of clinical laboratory parameters (and/or change from baseline in clinical laboratory parameters) will be presented for all scheduled measurements over time. Mean laboratory values over time will be plotted for key laboratory parameters.

Shift tables for laboratory parameters will be generated for changes in NCI CTCAE grade from baseline to the worst postbaseline value. Graphical displays of key safety parameters, such as scatter plots of baseline versus worst postbaseline values, may be used to understand the modakafusp alfa safety profile.

Descriptive statistics for the actual values (and/or the changes from baseline) of vital signs, weight and ECOG performance status scores will be tabulated by scheduled time points.

Physical examination findings will be presented in the data listings.

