6.7.1 Adverse Events

Adverse events will be coded using the Medical Dictionary for Regulatory Activities (MedDRA) Version 25.0 or later (based on the version at time of database lock) with the severity graded by the NCI CTCAE Version 5.0 or later (based on the version at time of database lock). Treatment-emergent is defined as any AE that occurs after administration of the first dose of any study drug through 30 days after the last dose of any study drug.

Treatment-emergent AEs will be summarized by MedDRA system organ class (SOC) and preferred term (PT) by dose level. For summary tabulations the following hematologic abnormalities coded to MedDRA preferred terms in the Investigations SOC will be pooled with the appropriate clinical terms in the Blood and lymphatic system disorders SOC:

MedDRA Preferred Term (Investigation SOC)	Mapped to (Blood and lymphatic system disorders SOC)
Neutrophil count decreased	Neutropenia
Platelet count decreased	Thrombocytopenia
Hemoglobin decreased	Anemia
White blood cell count decreased	Leukopenia
Lymphocyte count decreased	Lymphopenia

Summary tabulations will include the following categories by SOC/PT unless otherwise specified:

- Treatment-emergent AEs (by PT as well).
- Drug-related treatment-emergent AEs.

- Grade 3 or higher treatment-emergent AEs.
- Grade 3 or higher drug-related treatment-emergent AEs.
- Grade 3 and Grade 4 treatment-emergent AEs (based on maximum severity, by PT as well).
- Grade 5 treatment-emergent AEs.
- Grade 5 drug-related treatment-emergent AEs.
- The most commonly reported treatment-emergent AEs (i.e., those events reported by $\geq 10\%$ of all patients, by PT only).
- Serious treatment-emergent adverse events (SAEs) (based on maximum severity).
- Drug-related treatment-emergent SAEs.
- Grade 3 or higher treatment-emergent SAEs.
- Grade 3 or higher drug-related treatment-emergent SAEs.
- Grade 3 and Grade 4 treatment-emergent SAEs (based on maximum severity).
- Grade 3 and Grade 4 drug-related treatment-emergent SAEs (based on maximum severity).
- Treatment-emergent AEs resulting in discontinuation of study drug.
- Treatment-emergent AEs resulting in study drug modifications (including discontinuation, delay, reduction, and interruption).
- Treatment-emergent AEs resulting in dose delays.
- Treatment-emergent AEs resulting in dose reductions.
- Treatment-emergent AEs resulting in infusion rate reductions
- Treatment-emergent AEs resulting in drug interruptions.

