- Treatment-emergent AEs resulting in drug infusion interruptions.
- Treatment-emergent AESIs – all Grades (by PT as well).
- Treatment-emergent AESIs Grade 3 or Grade 4.
- Treatment-emergent AESIs Grade 5.
- Serious treatment-emergent AESIs.

All summaries will be by dose levels by phases (phase 1 escalation and phase 2a dose finding) for patients in the safety population.

Patients with the same AE more than once will have that event counted only once within each SOC, and once within each preferred term. Patients with the same AE more than once will have only the maximum intensity of that event counted once within each SOC, and once within each preferred term.

Most commonly reported (at least 10% of all patients) treatment-emergent AEs will be presented by preferred term only. Patients with multiple occurrences of the same AE will have that event counted only once within each preferred term.

An overall summary treatment-emergent AE table will include numbers and percentages of patients who had any treatment-emergent AE, drug-related treatment-emergent AE, Grade 3 or higher treatment-emergent AE, grade 3 or higher drug-related treatment-emergent AE, serious treatment-emergent AE, drug-related serious treatment-emergent AE, serious treatment-emergent AE leading to study drug discontinuation, treatment-emergent AE resulting in study drug discontinuation, and on-study deaths. On-study death is defined as deaths that occur between the first dose of study drug and up to 30 days after the last dose of study drug and deaths that occur more than 30 days after the last dose of study drug but are assessed as study drug-related.

A by-patient listing of DLTs as identified by the investigator that occur during Cycle 1 of treatment will be presented by dose levels for all patients enrolled during the phase 1 dose escalation portion of this study. Patients will be grouped by the dose level to which they were originally assigned, including those who receive subsequent treatment at a lower or higher dose level.

A by-patient listing of all deaths regardless of whether on study or not will also be presented. In this listing, on-study deaths will be flagged.

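### TEAE frequency is summarised by dose only as crude percentages over treatment periods of unequal length; common-window tables should be added beside them

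*Protocol*

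**What the plan says.** - **Endpoint.** Protocol 2.0 and 5.2.1 and SAP 1.2.1 give two phase 1 primary endpoints: DLT incidence and "Frequency and severity of treatment-emergent adverse events (TEAEs) according to the NCI CTCAE, Version 5.0".
- **Length of treatment.** "Patients may receive study drug treatment until they experience progressive disease, unacceptable toxicity, or other discontinuation criteria are met" (Protocol 2.0, repeated in 6.3.1). Table 6.a sets a maximum time frame of 60 months for "Primary: Frequency and severity of TEAEs".
- **Window.** SAP 6.7.1 counts "any AE that occurs after administration of the first dose of any study drug through 30 days after the last dose of any study drug". Protocol 13.1.8 tabulates "TEAEs that occur after administration of the first dose of study drug and through 30 days after the last dose of study drug" but also closes the window when a new anticancer therapy begins, if that is sooner. The SAP has no such stop.
- **Measure.** "An overall summary treatment-emergent AE table will include numbers and percentages of patients who had any treatment-emergent AE" (SAP 6.7.1). A patient counts once per term, and SAP 6.1 bases the denominator on the number of subjects. "All summaries will be by dose levels by phases (phase 1 escalation and phase 2a dose finding) for patients in the safety population".
- **Exposure.** SAP 6.5 and Protocol 13.1.8 summarise time on treatment by itself. Neither document plans TEAEs by cycle, in a fixed window, per unit of time at risk, or as time to first event.
- **Use.** Protocol 4.4 names three inputs to the phase 2a doses: Cycle 1 DLT data; then "Additional safety, tolerability, PK, and PD data as available from Cycle 1 and beyond in the phase 1 dose escalation"; then benefit-risk data from the monotherapy study. Protocol 6.1 bases the RP2D on integrated safety, efficacy, PK and PD. SAP 6.1 and 6.1.3 rule out formal comparisons between dose levels.

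**The concern.** A percentage of patients with an event depends on the event rate and on how long each patient was watched. Here the watching time is set by each patient's treatment duration and, at an interim look, by when the cohort opened. The tables are laid out by dose level, and somebody will read across the columns when choosing doses.

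Cycle 1 DLTs are protected because their window is the same at every dose. What follows Cycle 1 is not, and that is the period the second input in Protocol 4.4 reaches into. Infection and bleeding, which Protocol 4.3 names as possible clinical consequences of the overlapping cytopenias, need not be confined to the first cycles. For such events a dose observed for less time can look safer than one with the same rate observed for longer.

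**Working it through.** **1. The plan's own AE calculation.** The only AE-frequency figures are in Protocol 13.2 and SAP 4.0, for 20 patients per phase 2a arm. Formula: 1 − (1 − p)^20. For p = 5, 10, 15 and 20% this gives 64.15, 87.84, 96.12 and 98.85%, against the stated 64, 88, 96 and 99%. All reproduce. The calculation treats an AE rate as one fixed probability, with no time element. Nothing similar is given for phase 1.

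**2. Why windows are likely to be unequal at dose selection.** Under Protocol 8.4 and Table 8.a, escalation needs evaluated Cycle 1 data, at the least 3 of 3 patients without DLT and none pending. Each higher dose therefore opens at least one 28-day cycle after the one below. Going from 80 to 120 to 240 mg, the earliest 80 mg patients have at least two more cycles of potential follow-up than any 240 mg patient.

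**3. Steady-rate event, identical hazard at both doses.** The documents give no hazards or durations by dose, so both are assumed. Crude incidence = 1 − exp(−h × t). For c treated cycles, t = ((c − 1) × 28 + 30)/28, which places the last dose on Day 1 of the last cycle. For 3 cycles t = 86/28 = 3.07; for 12 cycles t = 338/28 = 12.07.

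| Hazard per cycle | 3 cycles | 12 cycles |
|---|---|---|
| 0.02 | 6.0% | 21.4% |
| 0.05 | 14.2% | 45.3% |
| 0.10 | 26.4% | 70.1% |
| 0.20 | 45.9% | 91.1% |

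The true rate ratio is 1.0 in every row. A daratumumab dose on Day 15 of Cycle 3 would lengthen the shorter window by 14 days (t = 100/28 = 3.57), giving 16% instead of 14% at h = 0.05.

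A shorter-term version follows from step 2. If 240 mg has just finished Cycle 1 and the windows are 3, 2 and 1 cycles at 80, 120 and 240 mg, then h = 0.05 gives 1 − exp(−0.15), 1 − exp(−0.10) and 1 − exp(−0.05), or 14%, 10% and 5%.

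**4. Early-onset event.** Protocol 4.5.1.2 reports that, at 1.5 mg/kg Q4W, mean platelets and neutrophils were lowest in the first two cycles. Assume a hazard of 0.35 per cycle in Cycles 1 and 2, then 0.01.

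- 3 cycles: cumulative hazard 0.70 + 0.01 × 1.07 = 0.711, crude 50.9%.
- 12 cycles: 0.70 + 0.01 × 10.07 = 0.801, crude 55.1%.

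The gap is about 4 points.

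**5. What each remedy does.** In a common Cycles 1 to 3 window, the step 3 doses agree: 14.2% for both at h = 0.05, 26.4% for both at h = 0.10. Exposure-adjusted rates also agree there, at 0.05 and 0.10 per patient-cycle.

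For the step 4 event they do not. Expected time at risk of a first event is (1 − exp(−0.70))/0.35 = 1.44 cycles over the first two, plus exp(−0.70) × (1 − exp(−0.01 × (t − 2)))/0.01 afterwards. The second part is 0.53 for 3 cycles and 4.76 for 12. The rates are 0.509/1.97 = 0.26 and 0.551/6.20 = 0.09 per patient-cycle, a ratio of about 2.9 between doses with identical hazards.

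**6. Precision.** With 6 patients, 14.2% and 45.3% correspond to 0.85 and 2.72 patients. The exact 95% CI for 2 of 6 is 4.3% to 77.7%.

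**The case against.** - **The tables are descriptive, and DLTs lead.** This stands. No formal comparison of doses is planned, Cycle 1 DLTs come first in Protocol 4.4, and later safety is one part of the second input, beside tolerability, PK and PD. A reader might infer that TEAE percentages are a main driver of dose choice; the documents do not say so. Nor do they say that the SAP 6.7.1 tables are the ones used at that decision. They also name no other measure for the later safety data.
- **The direction is not fixed.** This stands. It is tempting to say that lower doses will look more toxic because they are followed longest. But treatment ends at progression, and the monotherapy response rate was 30% (3 of 10) at 70 to 90 mg equivalents (Protocol 4.3) against 48% at 1.5 mg/kg, the 120 mg equivalent (Protocol 4.1.2.2). Lower-dose patients might stop sooner. A de-escalation cohort at 60 mg would open after 80 mg.
- **Staggered entry matters less at the end.** This stands. Protocol 6.3.2 places the final analysis after all patients have completed assessments or withdrawn. What remains then is different treatment duration, which is partly an effect of dose.
- **Cytopenias are already shown over time.** This stands for laboratory values: SAP 6.7.3 plans platelet and neutrophil profiles by dose level and means over time. It does not cover infection, bleeding, SAEs or AESIs.
- **Small cohorts swamp the effect.** Imprecision is the larger problem at 6 per dose level, but it does not remove a difference caused by follow-up.
- **Phase 2a may not open.** Appendix G, describing an unimplemented amendment, records a sponsor decision not to proceed to it. The current body text still plans it, and the phase 1 endpoint is affected either way.

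**Conclusion.** The point holds as a reporting gap that is cheap to close. The plan has no TEAE summary that puts dose levels on the same observation time, although TEAE frequency is a phase 1 primary endpoint and safety beyond Cycle 1 is a stated input to dose selection. For steady or late events the effect can be large: 14% versus 45% at an assumed 0.05 per cycle and 3 versus 12 cycles. For early cytopenias it is small: about 51% versus 55%. These sizes rest on assumed hazards and durations. The gap matters only if observation time differs by dose, which is likely at the dose-selection cut but not certain.

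Two stronger readings are not supported: that the plan will misrank the doses, and that exposure-adjusted rates should take the place of the crude percentages. The first depends on exposures and hazards the documents do not give. The second would create a roughly 2.9-fold artefact for front-loaded events, the pattern the protocol reports for blood counts.

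**What to change.** 1. **Reconcile the window first.** Protocol 13.1.8 ends it at subsequent anticancer therapy if that is earlier; SAP 6.7.1 does not. The two must agree before any time at risk is defined.
2. **Add common-window tables to SAP 6.7.1.** By dose level, beside the retained crude tables, give the incidence of TEAEs, Grade 3 or higher TEAEs, SAEs and AESIs within shared windows, for example Cycle 1 and Cycles 1 to 3, with the number of patients at risk at the start of each cycle. State whether windows are counted in cycles or in days from first dose: SAP 6.1.1.2 starts a cycle at each modakafusp alfa dose, so delays would stretch a cycle-based window.
3. **Say how they are used.** For the phase 2a and RP2D decisions, read doses against each other on the windows that all of them have reached. If one cohort has only finished Cycle 1, only the Cycle 1 window is shared.
4. **Optional supplement.** Show exposure-adjusted rates for events without early onset, not as a replacement for the crude percentages.

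The cost is a short SAP paragraph and a few descriptive tables from data already collected. The estimates will be imprecise at phase 1 cohort sizes.
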